12.5. Virology Analyses

Only data analyzed by the designated central virology laboratories will be used for any viral load analyses.

12.6. Safety Analyses

All safety analyses will be presented by randomized treatment arm using the safety analysis set. Inferential analyses will generally not be performed for safety endpoints; exceptions are defined herein or will be defined in the SAP.

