5. STUDY OBJECTIVES AND OUTCOME MEASURES

5.1. Primary Objective and Primary Efficacy Endpoint

The primary objective of this study is to compare the safety, overall tolerability, and virologic response of BCV vs. SoC for the treatment of AdV infection in high-risk pediatric allogeneic HCT recipients. A virologic response-driven approach to the duration of treatment will be evaluated, in which subjects randomized to BCV therapy are treated until AdV viremia is confirmed as undetectable or until a maximum of 16 weeks of therapy, whichever occurs first. The primary efficacy endpoint is the AAUC for AdV viremia (\log_{10} copies/mL) from randomization through Week 16 post-randomization.

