5.3.3. Safety Endpoints

- Incidence of treatment-emergent AEs (TEAEs), particularly those of \geq CTCAE Grade 3 severity and SAEs
- Incidence of treatment-related AEs, particularly those of \geq CTCAE Grade 3 severity and SAEs
- Incidence of AEs resulting in permanent BCV or other anti-AdV drug discontinuation
- Incidence of AEs requiring BCV or other anti-AdV drug interruption
- Incidence of AEs requiring dose modification or consolidation of BCV or other anti-AdV drug
- Incidence of fatal AEs
- Incidence of and time to CTCAE Grade 2 or higher diarrhea
- Incidence of doubling, tripling, or quadrupling of baseline serum creatinine
- Incidence of need for renal replacement therapy
- Incidence of $\geq 1/2/3$ CTCAE grade increases from baseline for safety laboratory parameters of interest (by visit, maximum on-treatment, last on-treatment, last on-study)
- Distributions of change from baseline over time for central safety laboratory parameters of interest (by visit, maximum on-treatment, last on-treatment, last on-study)
- Assessment of all deaths that occur through Week 16 and in follow up through Week 36

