12.6.1. Adverse Events

On-study AEs are those events that occur from Day 1 through Week 16. Only on-study AEs are summarized unless otherwise specified.

For the BCV arm, TEAEs are those events that begin on or after the date of the first dose of study drug and on or before 7 days after the date of the last dose of study drug. For the SoC arm, TEAEs are those that begin on or after Day 1 and on or before 7 days after the date of the last dose of anti-AdV therapy (or Week 16 if no anti-AdV therapy was used in SoC arm).

Follow-up AEs are those that begin beyond 7 days after the last dose of study drug through Week 16.

Summaries (number and percent of subjects) of AEs by system organ class and preferred term will be provided as follows:

- TEAEs
- \geq CTCAE Grade 3 TEAEs
- Treatment-emergent SAEs
- Treatment-related AEs
- \geq CTCAE Grade 3 treatment-related AEs
- Treatment-related SAEs
- AEs resulting in permanent BCV or other anti-AdV drug discontinuation
- AEs requiring BCV or other anti-AdV drug interruption
- AEs requiring dose modification or consolidation of BCV or other anti-AdV drug
- On-study AEs
- \geq CTCAE Grade 3 on-study AEs
- On-study SAEs
- Follow-up AEs
- \geq CTCAE Grade 3 follow-up AEs
- Follow-up SAEs
- SAEs starting after Week 16
- AEs beginning after Week 16 and leading to death

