12.6.2. Laboratory Results

Descriptive statistics (N, mean, standard deviation [SD], median, first and third quartiles [Q1, Q3], minimum, and maximum) will be provided for each continuous laboratory test by treatment arm. Values will be summarized at baseline, at each on-treatment time point, for the minimum and maximum on-treatment values, for the last on-treatment value, and for the last on-study value. These results will also be presented as boxplots.

Dichotomous laboratory endpoints will be descriptively analyzed using counts and percentages.

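### Comparing safety is part of the primary objective, yet apart from all-cause mortality no between-arm estimate with a confidence interval is named for renal, hepatic or diarrhea endpoints

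*Combined protocol and SAP*

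**What the plan says.** The aim is comparative. Section 5.1 states: "The primary objective of this study is to compare the safety, overall tolerability, and virologic response of BCV vs. SoC". Section 4.3.8 keeps SoC subjects off BCV until Week 16 partly so that safety can be compared between the arms.

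Section 5.3.3 lists the safety endpoints. They include "Incidence of doubling, tripling, or quadrupling of baseline serum creatinine", need for renal replacement therapy, rises of one, two or three "CTCAE grade increases from baseline for safety laboratory parameters of interest", and incidence of and time to Grade 2 or higher diarrhea.

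The method is in Section 12.6: "All safety analyses will be presented by randomized treatment arm using the safety analysis set". The next sentence reads "Inferential analyses will generally not be performed for safety endpoints" and continues "exceptions are defined herein or will be defined in the SAP". The Synopsis repeats the rule without the clause on exceptions. For adverse events, Section 12.6.1 says: "Summaries (number and percent of subjects) of AEs by system organ class and preferred term will be provided". For laboratory data, Section 12.6.2 says: "Dichotomous laboratory endpoints will be descriptively analyzed using counts and percentages".

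One outcome that bears on safety is treated differently. Section 12.4.1 compares all-cause mortality at Week 16 through the upper one-sided 95% bound of the BCV minus SoC difference, set against 10 percentage points.

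**The concern.** The objective asks for a comparison, and the stated method gives two percentages side by side. Section 4.3.7 says that the safety assessment should cover the GI toxicity known for oral BCV and the renal injury known for IV cidofovir, so these endpoints carry much of the benefit-risk argument. With 47 subjects in the control arm, a sizeable gap between percentages can be chance, and equal percentages can hide a sizeable true difference. A table of percentages shows neither.

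The second issue is timing. Section 12 allows documented SAP amendments until database lock for the primary analysis, and treatment is open-label (Section 8.8). While the exceptions are unnamed, the choice of safety endpoint and observation window for a between-arm estimate can be made after the arm-level experience is known.

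**Working it through.** **1. Figures in the plan.** No precision or power is stated for any safety comparison. The arm sizes come from the primary endpoint (Section 12.1 and Synopsis: 94 BCV, 47 SoC, SD 1.03, difference 0.6). The standard error is 1.03 × sqrt(1/94 + 1/47) = 0.184, and 0.6/0.184 = 3.26. At two-sided 0.05 (assumed for the primary test), power is Φ(3.26 − 1.96) = 0.903; the noncentral t gives 0.899. The stated power of more than 90% is reproduced by the normal approximation. The size was thus set on viremia, and safety precision is whatever follows from it.

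**2. What is planned between arms.**

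| Outcome | Planned between-arm analysis |
|---|---|
| All-cause mortality, Week 16 | Risk difference with one-sided 95% bound (12.4.1) |
| Dichotomous secondary efficacy | Common odds ratio with 95% CI (12.4.2) |
| Maximum PELOD score | Same ANCOVA as the primary endpoint (12.4.2); one aggregate over six organ systems |
| Creatinine doubling, ALT and bilirubin grade shifts | Counts and percentages by arm (12.6.2) |
| Renal replacement therapy | No method beyond the general rule in 12.6 |
| Diarrhea and other adverse events | Number and percent by arm (12.6.1) |
| Exposure-response for ALT and bilirubin | BCV subjects only, because it needs the PK set (12.2, 12.7) |

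The last row is not a between-arm comparison, so it does not fill the gap.

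**3. Windows.** Under Section 12.6.1, the treatment-emergent window in the BCV arm ends 7 days after the last dose. In the SoC arm it ends 7 days after the last anti-AdV dose, or at Week 16 if none was given. BCV stops at confirmed clearance (Section 8.3.1), so observation time can differ between arms. The laboratory summaries in Section 12.6.2 likewise rely largely on on-treatment values. The on-study window in Section 12.6.1, Day 1 through Week 16, is the same for both arms.

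**4. Precision at 94 and 47.** The Wald half-width is 1.96 × sqrt(p1(1 − p1)/94 + p0(1 − p0)/47). With equal observed rates of 15%, it is 1.96 × sqrt(0.1275/94 + 0.1275/47) = 1.96 × 0.0638 = 0.125, or 12.5 points.

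The rates below are figures the protocol quotes from other cohorts. They illustrate the range and do not predict this trial.

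| Rate, same in both arms | Source of rate | Half-width, points |
|---|---|---|
| 8.5% | Upper figure for dialysis after HCT (4.1) | 9.8 |
| 15% | Lower figure for creatinine doubling (4.1) | 12.5 |
| 39% | Renal toxicity on IV cidofovir, 9/23 (4.4) | 17.1 |
| 73% | Upper figure for creatinine doubling (4.1) | 15.5 |

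Newcombe intervals on whole counts (BCV minus SoC; all counts hypothetical) agree in scale:

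- 14/94 vs 7/47: 0 points (-14.0 to +11.4)
- 5/94 vs 7/47: -9.6 points (-22.7 to +0.4)
- 19/94 vs 18/47: -18.1 points (-33.9 to -2.6)

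The Grade 3 or higher diarrhea rates in Section 4.2.3.1 (14% vs 6%) are 2/14 vs 1/18 against placebo in another study. They are too sparse to serve as planning rates here.

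**The case against.** The case on the other side is substantial.

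- **The plan does not rule inference out.** Section 12.6 says that it will generally not be done and reserves exceptions. Section 12 leaves detailed methods to a SAP, and the document supplied contains the protocol's statistics section but no separate SAP. A reader might infer that the trial has no such estimates at all; that cannot be shown from this text.
- **The gravest safety outcome is already covered.** All-cause mortality has an interval-based comparison, which Section 4.3.7 says is there to rule out harm. PELOD, with creatinine, AST and INR components, also gets a between-arm analysis.
- **The tables can be read.** A reader might infer that the renal and hepatic comparison is uninterpretable. It is not: counts by arm are enough to derive an unadjusted risk difference and interval. No data are lost and no result is biased by the omission.
- **Time to diarrhea may have a method.** The Synopsis mentions Kaplan-Meier and Cox methods for most time-to-event analyses without limiting them to efficacy. In the body, that text sits under secondary efficacy (Section 12.4.2), so its reach is unclear.

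These arguments limit the point but do not remove it. A reader can compute an interval but cannot supply pre-specification of endpoint and window. PELOD is an aggregate and does not isolate renal or hepatic harm. The exceptions clause names none of the endpoints at issue.

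**Conclusion.** The point stands as a cheap improvement. The protocol states a comparative safety objective. Apart from all-cause mortality, the available text names no between-arm estimate with a confidence interval for renal, hepatic or diarrhea endpoints, and it leaves any exceptions to the SAP. What is missing is a pre-specified statement of precision over a common window. At 94 and 47 subjects that imprecision is material: over the illustrative rates used, the 95% half-width under equal rates runs from about 10 to 17 points.

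This assumes that every subject randomized to BCV is dosed, so that the safety set matches the planned arm sizes, and that estimates are unadjusted. If the separate SAP already names these estimates and a Week 16 window, the point is closed apart from aligning the protocol text.

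**What to change.** In Section 12.6, name the exceptions now and mirror them in the Synopsis and SAP:

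- Grade 2 or higher diarrhea
- on-study adverse events of Grade 3 or higher
- on-study serious adverse events
- doubling of baseline serum creatinine
- renal replacement therapy
- increases of two or more CTCAE grades in ALT
- increases of two or more CTCAE grades in total bilirubin

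For each, report the BCV minus SoC risk difference with a two-sided 95% confidence interval (score or Newcombe method) in the safety analysis set. Use Day 1 through Week 16 in both arms instead of the treatment-emergent or on-treatment windows. Present these as estimates, without p-values or any alpha claim.

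The cost is SAP wording and a few table rows; no new data or subjects are needed. The downside is several intervals without multiplicity control, which the table footnote should say.

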12.6.1. Adverse Events

On-study AEs are those events that occur from Day 1 through Week 16. Only on-study AEs are summarized unless otherwise specified.

For the BCV arm, TEAEs are those events that begin on or after the date of the first dose of study drug and on or before 7 days after the date of the last dose of study drug. For the SoC arm, TEAEs are those that begin on or after Day 1 and on or before 7 days after the date of the last dose of anti-AdV therapy (or Week 16 if no anti-AdV therapy was used in SoC arm).

Follow-up AEs are those that begin beyond 7 days after the last dose of study drug through Week 16.

Summaries (number and percent of subjects) of AEs by system organ class and preferred term will be provided as follows:

- TEAEs
- \geq CTCAE Grade 3 TEAEs
- Treatment-emergent SAEs
- Treatment-related AEs
- \geq CTCAE Grade 3 treatment-related AEs
- Treatment-related SAEs
- AEs resulting in permanent BCV or other anti-AdV drug discontinuation
- AEs requiring BCV or other anti-AdV drug interruption
- AEs requiring dose modification or consolidation of BCV or other anti-AdV drug
- On-study AEs
- \geq CTCAE Grade 3 on-study AEs
- On-study SAEs
- Follow-up AEs
- \geq CTCAE Grade 3 follow-up AEs
- Follow-up SAEs
- SAEs starting after Week 16
- AEs beginning after Week 16 and leading to death

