7.3. Subject Withdrawal Criteria

Subjects randomized to receive BCV must be managed according to the toxicity management criteria described in Section 8.3.2. Subjects randomized to the SoC arm will be managed according to local or institutional practice guidelines and any relevant product labelling.

Subjects randomized to BCV who experience any of the following criteria after initiating treatment in this study will be required to discontinue BCV, but will continue to be followed in the study:

- Subject request to discontinue for any reason
- TEAE that necessitates the discontinuation of BCV as described in Section 8.3.2
- If the investigator or the subject's primary care provider believes that participation in the study is no longer in the best interests of the subject
- Pregnancy in a female subject

Female subjects who become pregnant will be immediately discontinued from BCV, but will continue to be followed in the study. See Section 11.9.5 for actions to take and reporting requirements for pregnancy. Pregnancies in female subjects randomized to the SoC arm must be reported according to local guidelines and relevant product labelling.

- Discontinuation of the study at the request of Chimerix, a regulatory agency, or the governing institutional review board, research ethics board, or independent ethics committee (collectively referred to as "ethics committee" [EC])

In addition, if any of the following criteria are met, BCV will be discontinued at the discretion of the investigator, in consultation with the Chimerix Medical Monitor (or designee):

- Development of an exclusionary condition, including a decrease in eGFR to < 15 mL/min considered related to BCV, or unrelated to BCV but not being dialyzed; see Section 8.3.2.6
- Treatment with, or requirement for treatment with, a prohibited or excluded medication; see Section 8.6.1.1
- Subject is not compliant with the protocol (i.e., significant protocol deviation)

All subjects who are randomized will be followed in the study through completion of the Week 36 assessment, including subjects who discontinue BCV for any reason and subjects who are randomized but not dosed in either arm. The subjects will be managed at the discretion of the responsible investigator according to local SoC, but will continue to be monitored in accordance with the Schedule of Study Assessments/Procedures (see Section 6.2).

Subjects who are randomized and who do not complete the study will not be replaced.

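### Treatment-emergent AE incidence is counted over windows that differ by arm and follow treatment length, so it cannot serve as the between-arm safety comparison; the on-study AEs already defined in 12.6.1 should be named for that purpose

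*Combined protocol and SAP*

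**What the plan says.** Section 5.1 states: "The primary objective of this study is to compare the safety, overall tolerability, and virologic response of BCV vs. SoC". Section 5.3.3 then lists, among the safety endpoints, "Incidence of treatment-emergent AEs (TEAEs), particularly those of" Grade 3 or higher severity and SAEs.

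Section 12.6.1 gives the TEAE window three possible ends:

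- BCV arm: events from first dose that begin "on or before 7 days after the date of the last dose of study drug".
- SoC arm, treated: events from Day 1 that begin "on or before 7 days after the date of the last dose of anti-AdV therapy".
- SoC arm, untreated: "or Week 16 if no anti-AdV therapy was used in SoC arm".

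The same section defines on-study AEs as those from Day 1 through Week 16 in either arm, and says: "Only on-study AEs are summarized unless otherwise specified". The tables are "Summaries (number and percent of subjects) of AEs by system organ class and preferred term", first for TEAEs and later for on-study AEs, on-study Grade 3 or higher AEs and on-study SAEs. On-study incidence is not in the 5.3.3 endpoint list. No section says which set of tables is the comparison between arms, and no exposure-adjusted rate is planned.

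Window length follows from treatment. BCV stops once clearance is confirmed (8.3.1) and may be restarted (8.4). The synopsis leaves SoC duration to local practice, and 4.3.6 allows SoC that is not an antiviral drug. After BCV is stopped, 7.3 provides: "The subjects will be managed at the discretion of the responsible investigator according to local SoC".

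**The concern.** A proportion with at least one event rises with the time over which events are counted. If the counting time differs between arms, equal event rates produce unequal percentages. Here it differs by design: BCV duration is driven by virologic response, SoC duration is local, and an SoC subject who receives no antiviral drug is counted for the full 16 weeks.

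The anchors also differ in kind. The BCV window follows study drug only, so anti-adenovirus drugs given after BCV stops do not extend it. The SoC window follows the last dose of any anti-adenovirus therapy. Section 8.6.1.1 bars cidofovir (CDV) only while BCV is being taken, so such later treatment is possible.

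What is at stake is the reading of a named safety endpoint in an open-label trial whose primary objective includes a safety comparison. A difference, or its absence, could reflect observation time rather than toxicity.

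**Working it through.** The protocol gives no TEAE rate, so there is no planned figure to reproduce. The check asks what the windows alone do when the arms have the same event hazard.

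**Formula.** With a constant hazard and 16-week (112-day) risk R, the chance of at least one event in w days is P(w) = 1 - (1 - R)^(w/112). R is not in the documents. I assume 40% and vary it below.

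**Window lengths**

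- BCV, clearance at Week 4: 28 days + 7 to 14 to confirm (8.3.1) + 7 = 42 to 49 days.
- BCV, clearance at Week 6: 42 + 7 to 14 + 7 = 56 to 63 days.
- SoC on IV CDV: 63 + 7 = 70 days, from the 9-week median time to clearance in the retrospective cohort described in 4.4, where patients were treated until viremia cleared.
- SoC untreated, or BCV continued to Week 16: 112 days.

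**Single windows, R = 40%**

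| Window (days) | 42 | 49 | 56 | 63 | 70 | 112 |
|---|---|---|---|---|---|---|
| P(w) | 17.4% | 20.0% | 22.5% | 25.0% | 27.3% | 40.0% |

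**BCV mix.** Section 4.3.3.1 reports 59% undetectable by Week 4 and 68% by Week 6 in the earlier single-arm study, with denominators of 69 and 66, so the combination is illustrative. I take 59% clearing at Week 4, 9% at Week 6, and the remaining 32% dosed to Week 16, which is an upper bound for that group.

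- Confirmation at 7 days: 0.59 × 17.4 + 0.09 × 22.5 + 0.32 × 40 = 25.1%.
- Confirmation at 14 days: 0.59 × 20.0 + 0.09 × 25.0 + 0.32 × 40 = 26.9%.

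**SoC, untreated share u, treated window 70 days.** (1 - u) × 27.3 + u × 40 gives 27.3% at u = 0 and 33.7% at u = 0.5. The values of u are assumptions.

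**BCV minus SoC with no true difference**

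- Smallest gap: 26.9 - 27.3, about -0.5 point unrounded (-0.4 from the rounded percentages).
- Largest gap: 25.1 - 33.7 = -8.6 points.

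**Reversal.** With a 42-day treated SoC window and u = 0, the 7-day mix gives 25.1 - 17.4 = +7.7 points. At u = 0.5, SoC is 28.7% and the difference is -3.6.

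**Sensitivity to R** (7-day mix, 70-day SoC window, u from 0 to 0.5): -0.9 to -4.4 points at R = 20%; -3.9 to -12.1 at R = 60%.

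**Sensitivity to hazard shape.** Replacing w/112 by (w/112)^k, the gap between single 42- and 70-day windows is 9.9 points at k = 1, 6.4 for a front-loaded hazard (k = 0.5; 26.9% vs 33.2%) and 11.2 for a back-loaded one (k = 2; 6.9% vs 18.1%).

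**Anchor example.** A BCV subject stops on Day 21 and then receives IV CDV to Day 91. The window is 21 + 7 = 28 days, P = 12.0%. An SoC subject on IV CDV to Day 91 has 91 + 7 = 98 days, P = 36.0%.

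**On-study window.** Counting Day 1 to Week 16 in both arms gives the same percentage when hazards are equal. One small asymmetry remains. AE recording starts at first dose in the BCV arm (11.9.1), up to 24 hours after randomization (6.4): P(111) = 39.7% against 40.0%, about 0.3 point. The data will exist, because AEs are recorded through Week 16 in both arms (11.9.1) and subjects who stop BCV stay on the visit schedule (6.2).

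**The case against.** Most of the remedy is already in the plan. On-study AEs are the default for AE summaries, their tables are listed, and no event is lost. By that default, other AE endpoints in 5.3.3, such as Grade 2 or higher diarrhea, already have the fixed window. Section 12.6 says safety is generally not tested, and Section 12 leaves detailed methods to a separate SAP. All of this stands, and it limits the consequence. It does not remove the point, because TEAE incidence is the named endpoint, on-study incidence is not, and the TEAE windows are a stated rule rather than a detail left open.

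On-study incidence has weaknesses too. It counts events long after the last BCV dose, including those due to later anti-adenovirus drugs, and the 16% to 24% of subjects expected to die by Week 16 (12.4.1) still have shortened observation. This is a reason to keep the TEAE tables, not to compare arms with them.

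Three stronger readings are not supported:

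- A reader might infer that TEAE incidence ranks as the main safety endpoint because it heads the list. Section 5.3.3 states no hierarchy.
- A reader might infer that the definition favors BCV. The documents do not give SoC treatment mix, SoC duration or re-treatment frequency for this trial, and plausible values give either sign.
- A reader might quote a much larger artefact by giving every BCV subject a 42-day window and half the SoC arm no therapy, or every SoC subject a very short course. The 59% figure in 4.3.3.1 does not fit the first. The 3 to 15 week clearance range for IV CDV in 4.4 gives no basis for the second across a whole arm.

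**Conclusion.** The point holds as a defect in how one named endpoint is defined for comparison. Followed as written, TEAE percentages in the two arms are not like for like. The illustrative artefact of about -0.5 to -8.6 points rests on equal constant hazards, an assumed 40% 16-week risk, clearance figures borrowed from earlier cohorts and an assumed 0% to 50% untreated SoC. It is not a forecast.

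The effect is confined to reading AE tables between arms. The primary virologic endpoint and the mortality endpoints do not use the TEAE window. The change should be made before the primary database lock, after which Section 12 allows no SAP amendment.

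**What to change.** 1. In 5.3.3 and 12.6.1, state that on-study (Day 1 to Week 16) incidence of AEs, Grade 3 or higher AEs and SAEs is the between-arm safety comparison. Keep the TEAE tables as a secondary, on-treatment description.
2. With the TEAE tables, show the median and range of window length and the total subject-weeks in each arm, so that the difference in observation time is visible.

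As a clarification only, add SoC wording to the definition of follow-up AEs, which is tied to study drug alone.

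The cost is wording and a small derivation. No new data or visits are needed, and the on-study tables are already listed. Section 12.8.4 already summarizes BCV duration from first to last dose, which gives most of the BCV window; the SoC counterpart is what has to be added. Item 2 could sit in the separate SAP. The price is the looser link to drug described above, which the retained TEAE tables address.
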